#### **11.2.1 Treatment-Emergent Adverse Events**

Treatment-emergent AEs are defined as any AE with an onset date that is after the first dose of study drug and no more than 30 days after the last dose of study drug. Events where the onset date is the same as the study drug start date are assumed to be treatment-

emergent. If an incomplete onset date was collected for an AE, the event will be assumed to be treatment-emergent, unless there is other evidence that confirms that the event was not treatment-emergent (e.g., the event end date was prior to the study drug start date).

### **11.2.2 Tabulations of Treatment-Emergent Adverse Events**

The number and percentage of subjects with treatment-emergent AEs will be tabulated by primary MedDRA System Organ Class (SOC) and preferred term. The SOCs will be presented in alphabetical order, and the preferred terms will be presented in alphabetical order within each SOC.

Subjects reporting more than one AE for a given preferred term will be counted only once for that term (most severe/highest grade incident for the severity tables and most related incident for the relationship tables). Subjects reporting more than one AE within a SOC will be counted only once for that SOC. Subjects reporting more than one AE will be counted only once in the overall total.

#### **Adverse Event Overview**

An overview of AEs will be presented consisting of the number and percentage of subjects experiencing at least one event for each of the following AE categories; this overview will also be presented for the set of HCV/HIV co-infected subjects within the populations/groups specified in Section 11.1:

- Any treatment-emergent AE;
- Treatment-emergent AEs with a "reasonable possibility" of being related to DAAs (ABT-493/ABT-530);
- Treatment-emergent AEs of Grade 3 or higher;
- Treatment-emergent AEs of Grade 3 or higher with a "reasonable possibility" of being related to DAAs (ABT-493/ABT-530);
- Serious treatment-emergent AEs;
- Serious treatment-emergent AEs with a "reasonable possibility" of being related to DAAs (ABT-493/ABT-530);

- Treatment-emergent AEs leading to discontinuation of study drug;
- DAA-related treatment-emergent AEs leading to discontinuation of study drug;
- Serious treatment-emergent AEs leading to discontinuation of study drug;
- Treatment-emergent AEs leading to interruption of study drug;
- Treatment-emergent AEs leading to death;
- Deaths.

### **Adverse Events by SOC and Preferred Term**

The following summaries of AEs by SOC and preferred term will be generated:

- Treatment-emergent AEs (will also be presented for the set of HCV/HIV co-infected subjects);
- Treatment-emergent AEs with a "reasonable possibility" of being related to DAAs (ABT-493/ABT-530);
- Serious treatment-emergent AEs;
- Serious treatment-emergent AEs with a "reasonable possibility" of being related to DAAs (ABT-493/ABT-530);
- Treatment-emergent AEs of Grade 3 or higher;
- Treatment-emergent AEs of Grade 3 or higher with a "reasonable possibility" of being related to DAAs (ABT-493/ABT-530);
- Treatment-emergent AEs leading to discontinuation of study drug;
- DAA-related treatment-emergent AEs leading to discontinuation of study drug;
- Serious treatment-emergent AEs leading to discontinuation of study drug;
- Treatment-emergent AEs leading to interruption of study drug;
- Treatment-emergent AEs leading to death.

A listing of treatment-emergent AEs grouped by SOC and preferred term with subject numbers will be created.

### **Adverse Events by Preferred Term**

The following summaries of AEs tabulated according to preferred term and sorted by overall frequency will be generated:

- Treatment-emergent AEs (will also be presented for the set of HCV/HIV co-infected subjects within the populations/groups specified in Section 11.1);
- Treatment-emergent AEs with a "reasonable possibility" of being related to DAAs (ABT-493/ABT-530);
- Serious treatment-emergent AEs;
- Serious treatment-emergent AEs with a "reasonable possibility" of being related to DAAs (ABT-493/ABT-530);
- Treatment-emergent AEs of Grade 3 or higher;
- Treatment-emergent AEs of Grade 3 or higher with a "reasonable possibility" of being related to DAAs (ABT-493/ABT-530).

### **Adverse Events by Maximum Severity Grade Level**

Treatment-emergent AEs and DAA-related treatment-emergent AEs will be summarized by maximum severity grade level of each preferred term. Each AE will be assigned a grade level (Grade 1, 2, 3, 4, or 5) by the investigator. If a subject has an AE with unknown severity, then the subject will be counted in the severity grade level category of "unknown," even if the subject has another occurrence of the same event with a severity present. The only exception is if the subject has another occurrence of the same AE with the highest grade level (Grade 5). In this case, the subject will be counted under the "Grade 5" category.

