6.1.3 Relationship to Study Drug

The investigator will use the following definitions to assess the relationship of the AE to the use of study drug:

Reasonable Possibility	An adverse event where there is evidence to suggest a causal relationship between the study drug and the adverse event.
No Reasonable Possibility	An adverse event where there is no evidence to suggest a causal relationship between the study drug and the adverse event.

For causality assessments, events assessed as having a reasonable possibility of being related to the study drug will be considered "associated." Events assessed as having no reasonable possibility of being related to study drug will be considered "not associated." In addition, when the investigator has not reported a causality or deemed it not assessable, AbbVie will consider the event associated.

[figure not shown]
If an investigator's opinion of no reasonable possibility of being related to study drug is given, an "Other" cause of event must be provided by the investigator for the serious adverse event.

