8.1.5.1 Adverse Events

Adverse events (AEs) will be coded using the Medical Dictionary for Regulatory Activities (MedDRA). The number and percentage of subjects with treatment-emergent AEs (i.e., any event that begins or worsens in severity after initiation of study drug through 30 days post-study drug dosing) will be tabulated by primary MedDRA System Organ Class (SOC) and preferred term. The tabulation of the number of subjects with treatment-emergent AEs by severity grade and relationship to each study drug (DAAs) also will be provided. Subjects reporting more than one AE for a given MedDRA preferred term will be counted only once for that term using the event with the most severe grade from the severity grade table and the most related event from the relationship to study drug tables. Subjects reporting more than one type of event within a SOC will be counted only once for that SOC.

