### **Adverse Events by Maximum Relationship**

Treatment-emergent AEs also will be summarized by maximum relationship of each preferred term to study drug (DAAs), as assessed by the investigator. If a subject has an AE with unknown relationship, then the subject will be counted in the relationship category of "unknown," even if the subject has another occurrence of the same event with

a relationship present. The only exception is if the subject has another occurrence of the same AE with a relationship assessment of "Reasonable Possibility." In this case, the subject will be counted under the "Reasonable Possibility" category.

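### SAP 11.2.2 lets one ungraded occurrence override a recorded Grade 3 or 4 event in the maximum-severity tables, against the most-severe-grade rule in the protocol and in the SAP itself

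*SAP*

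**What the plan says.** **Severity.** Protocol 8.1.5.1 plans a tabulation by severity grade in which a subject with repeated events of one preferred term is "counted only once for that term using the event with the most severe grade". The opening part of SAP 11.2.2 repeats this, taking the "most severe/highest grade incident for the severity tables and most related incident for the relationship tables". The later subsection of SAP 11.2.2, Adverse Events by Maximum Severity Grade Level, then gives a rule for missing grades: "If a subject has an AE with unknown severity, then the subject will be counted in the severity grade level category of" *unknown*. It applies even when a different occurrence of the same event has a grade, and the sole exception is a Grade 5 occurrence. The rule covers two sets of tables: all treatment-emergent events and DAA-related treatment-emergent events.

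Events of Grade 3 or higher also have their own summaries in SAP 11.2.2: in the overview, by SOC and preferred term, and by preferred term. The missing-grade rule is not written for these.

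**Causality.** Protocol 6.1.3 states that "when the investigator has not reported a causality or deemed it not assessable, AbbVie will consider the event associated". In SAP 11.2.2, Adverse Events by Maximum Relationship, the table is based on the investigator's assessment, and: "If a subject has an AE with unknown relationship, then the subject will be counted in the relationship category of" *unknown*, unless another occurrence of the same event is rated a reasonable possibility. The related-event lines of the overview and of the SOC and preferred-term summaries are defined by a reasonable possibility rating or as DAA-related. They carry no rule for missing causality.

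SAP 12.1 lists 16 changes from the protocol. Neither of these rules is among them.

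**The concern.** The missing-grade rule discards information that the study has collected. If one occurrence is recorded as Grade 3 and another has no grade, the maximum is at least Grade 3. Calling the subject unknown drops that lower bound. A programmer cannot follow this rule and the most-severe rule for the same subject.

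Repeated records of one term are expected by design, because Protocol 6.1.1.1 requires a worsening event to be reported as a new adverse event. An event that progresses to Grade 3 thus creates the pair of records to which the rule applies, should one of them lack a grade.

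Safety is one of the primary objectives (Protocol 4.1), and the study has a single arm, so the adverse event tables have no comparator to put them in context. A maximum-severity table that shows fewer Grade 3 or 4 subjects for a term than the Grade 3-or-higher summary in the same report would have to be explained. For causality, the stake is that events the sponsor says it considers associated may appear in no related-event summary.

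**Working it through.** The plan gives no figure on this point: no expected event rate and no rate of missing grade or causality. The check is therefore to apply the written rules to each possible pair of occurrences.

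**Step 1. Severity: one graded and one ungraded occurrence of the same term in one subject.** The most-severe rule is applied to the recorded grade.

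| Occurrences | SAP maximum-severity rule | Most-severe rule (Protocol 8.1.5.1; SAP 11.2.2 general rule) | Qualifies for the Grade 3-or-higher summaries on the recorded grade |
|---|---|---|---|
| Grade 1 + ungraded | unknown | Grade 1 | no |
| Grade 2 + ungraded | unknown | Grade 2 | no |
| Grade 3 + ungraded | unknown | Grade 3 | yes |
| Grade 4 + ungraded | unknown | Grade 4 | yes |
| Grade 5 + ungraded | Grade 5 | Grade 5 | yes |

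The two rules differ for Grades 1 to 4. For Grades 3 and 4, the maximum-severity table also differs from the Grade 3-or-higher summaries.

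**Step 2. Causality.**

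| Occurrences | SAP maximum-relationship table | Sponsor convention, Protocol 6.1.3 |
|---|---|---|
| missing only | unknown | associated |
| no reasonable possibility + missing | unknown | associated |
| reasonable possibility + missing | reasonable possibility | associated |
| no reasonable possibility only | no reasonable possibility | not associated |

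A known related event is never hidden. The first two rows differ. Read literally, those subjects also fall outside the summaries defined by a reasonable possibility rating.

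**Step 3. Size of one reclassified subject in a preferred-term row.**

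- All subjects, planned N about 160 (SAP 4.3): 1/160 = 0.6 percentage points.
- China, reported separately (SAP 11.1), planned N about 60 + 36 + 24 = 120 (SAP 4.2): 1/120 = 0.8 percentage points.

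**Step 4. How often a known Grade 3 or 4 event would be displaced.** This rests on an assumption, not on a figure in the documents. Suppose each other occurrence of the term lacks a grade independently with probability q, and the subject has m other occurrences. The probability of being moved to unknown is 1 − (1 − q)^m.

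- q = 0.5%, m = 1: 1 − 0.995 = 0.5%.
- q = 5%, m = 3: 1 − 0.95³ = 14.3%.

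This range applies only to subjects who have a Grade 3 or 4 occurrence and at least one other occurrence of the same term.

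**The case against.** The best defence is that the two SAP rules follow one convention: the maximum of a set with a missing member is unknown unless the known value is already the top category (Grade 5, or a reasonable possibility). Neither Protocol 8.1.5.1 nor the general rule in SAP 11.2.2 addresses a missing grade, so the later subsection could be read as filling a gap. For Grade 1 or 2 plus an ungraded occurrence this has force, because the ungraded event could be worse, and showing the known grade may understate it. For Grade 3 or 4 it has little: the event is already known to be severe, and the table loses that fact.

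A reader might infer that severe events are understated across the report. The documents do not support this. The rule reaches only the maximum-severity tables, the Grade 3-or-higher summaries keep the event, and the subject still appears under unknown. A reader might also infer that the rules always favour the drug. They do not: Grade 1 and 2 subjects also move to unknown, as do subjects with a no-reasonable-possibility rating plus a missing one.

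Missing grades should also be uncommon. Protocol 6.1 and 6.1.2 require severity to be assessed and graded for each event, and Protocol 10.2 and 11.0 provide for completeness review and data checks. That limits how often the rule applies but does not resolve the conflict.

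On causality the defence is stronger. Protocol 6.1.3 states a sponsor convention and names no table. The SAP relationship table reports the investigator's view, for which unknown is accurate. Protocol 8.1 allows no imputation in safety analyses. What remains is that the SAP does not say where, if anywhere, the Protocol 6.1.3 convention is applied.

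**Conclusion.** The severity point holds. The missing-grade rule in SAP 11.2.2 conflicts with Protocol 8.1.5.1 and with the general rule in the same SAP section, and SAP 12.1 does not declare it. It removes a recorded Grade 3 or 4 event from its grade in the maximum-severity tables, which can then disagree with the Grade 3-or-higher summaries. It is confined to those tables and to subjects with both graded and ungraded occurrences of one term. Each such subject is worth 0.6 points of a preferred-term row at N = 160. The total cannot be derived without a missingness rate.

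The causality point is secondary. It is an unreconciled difference between Protocol 6.1.3 and the SAP's related-event summaries, not an error in the investigator-assessed table. That such events drop out of the related summaries follows from a literal reading, since no missing-value rule is given there.

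Both conclusions assume that the two administrative changes named in the SAP Introduction did not alter Protocol 6.1.3 or 8.1.5.1. It is not evident whether the protocol text reviewed includes them.

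**What to change.** **Severity.** In SAP 11.2.2, Adverse Events by Maximum Severity Grade Level, classify each subject by the highest grade recorded for the term, and use unknown only when no occurrence of the term has a grade. At minimum, do this whenever a Grade 3 or 4 occurrence is recorded. No imputation is involved, since only recorded grades are used. The cost is one sentence and one programming condition. The small downside is that a subject with a Grade 1 or 2 occurrence and an ungraded one is shown at the known grade. A footnote counting subjects with any ungraded occurrence of the term would flag this.

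**Causality.** Keep the maximum-relationship table as the investigator-assessed table. In the overview and the SOC and preferred-term summaries of related events, either count unreported or non-assessable causality as related, following Protocol 6.1.3, or add that count as a second tabulation. The second option also avoids a dispute over the no-imputation statement in Protocol 8.1. The cost is a sentence or two and one further condition; related counts may rise slightly.

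List in SAP 12.1, with a reason, any departure from Protocol 8.1.5.1 or 6.1.3 that is kept.

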### **Adverse Events by Maximum Relationship**

Treatment-emergent AEs also will be summarized by maximum relationship of each preferred term to study drug (DAAs), as assessed by the investigator. If a subject has an AE with unknown relationship, then the subject will be counted in the relationship category of "unknown," even if the subject has another occurrence of the same event with

a relationship present. The only exception is if the subject has another occurrence of the same AE with a relationship assessment of "Reasonable Possibility." In this case, the subject will be counted under the "Reasonable Possibility" category.

### **Adverse Events of Special Interest**

The AEs of special interest include the following:

- "Hepatic Decompensation and Hepatic Failure" defined by the Product MedDRA Query (PMQ);
- "Hepatocellular Carcinoma" defined by the MedDRA preferred terms: hepatocellular carcinoma, hepatic neoplasm, hepatic cancer, hepatic cancer recurrent, and hepatic cancer metastatic.

For the hepatic decompensation/hepatic failure AE of special interest, the number and percentage of subjects experiencing at least one treatment-emergent AE in the search will be presented by SOC and preferred term and across all SOCs/preferred terms. In addition, a by-subject listing of treatment-emergent AEs meeting the search criterion will be provided.

For the hepatocellular carcinoma AE of special interest, a by-subject listing of all post-baseline (i.e., including both treatment-emergent and non-treatment emergent) AEs meeting the search criterion will be provided.

### **Adverse Events by HIV-1 ART Regimen**

For the HCV/HIV co-infected subjects who were on HIV-1 ART at initiation of study drug, treatment-emergent AEs also will be summarized for the subgroups defined by the HIV-1 ART regimen (e.g., RAL, DTG, RPV) the subjects were receiving at study drug initiation. For each HIV-1 ART regimen, the number and percentage of subjects experiencing treatment-emergent AEs will be tabulated according to SOC and preferred term.

### **AIDS-Associated Opportunistic Infections**

The number and percentage of subjects experiencing treatment-emergent AIDS-associated OIs will be tabulated according to SOC and preferred term for the HCV/HIV co-infected subjects (determined at Screening). Subjects reporting more than one AIDS-associated OI for a given preferred term will be counted only once for that term. Subjects reporting more than one AIDS-associated OI within a SOC will be counted only once for that SOC. Subjects reporting more than one AIDS-associated OI will be counted only once in the overall total.

#### **11.2.3 Listings of Adverse Events**

The following listings of AEs will be prepared:

- All serious AEs (from the time the subject signed the study-specific informed consent through the end of the study),
- Treatment-emergent serious AEs,
- Treatment-emergent AEs leading to death,
- Treatment-emergent AEs leading to discontinuation of study drug,
- Treatment-emergent AEs leading to study drug interruption,
- AEs (treatment-emergent or all, as applicable) in each of the AEs of special interest categories,
- Treatment-emergent AIDS-associated OIs.

#### **11.3 Analysis of Laboratory Data**

Data collected from the central and local laboratories, including additional laboratory testing due to a serious AE, will be used in all analyses.

##### **11.3.1 Variables and Criteria Defining Abnormality**

Hematology variables to be summarized include: hematocrit, hemoglobin, red blood cell (RBC) count, white blood cell (WBC) count, neutrophils, bands, lymphocytes, monocytes, basophils, eosinophils, platelet count, reticulocyte count, prothrombin time

(PT), international normalized ratio (INR), and activated partial thromboplastin time (aPTT).

Chemistry variables to be summarized include: blood urea nitrogen (BUN), creatinine, total bilirubin, direct and indirect bilirubin, alanine aminotransferase (ALT), aspartate aminotransferase (AST), alkaline phosphatase, sodium, potassium, calcium, inorganic phosphorus, uric acid, cholesterol, total protein, glucose, triglycerides, albumin, chloride, bicarbonate, magnesium, total insulin, gamma-glutamyl transferase (GGT), alpha fetoprotein, creatinine clearance (calculated using Cockcroft-Gault), estimated glomerular filtration rate (eGFR) calculated using the modification of diet in renal disease (MDRD) formula modified for the Chinese population (C-MDRD), and creatine phosphokinase (CPK).

Urinalysis variables to be summarized include: specific gravity and pH.

The definitions of toxicity grades for laboratory parameters are presented in [Table 11](#).

**Table 11. Definitions of Toxicity Grades 1, 2, 3, and 4 for Laboratory Values**

Test	Grade 1	Grade 2	Grade 3	Grade 4
ALT	> ULN – 3 × ULN	> 3 – 5 × ULN	> 5 – 20 × ULN	> 20 × ULN
AST	> ULN – 3 × ULN	> 3 – 5 × ULN	> 5 – 20 × ULN	> 20 × ULN
Alkaline Phosphatase	> ULN – 2.5 × ULN	> 2.5 – 5 × ULN	> 5 – 20 × ULN	> 20 × ULN
GGT	> ULN – 2.5 × ULN	> 2.5 – 5 × ULN	> 5 – 20 × ULN	> 20 × ULN
Total Bilirubin	> ULN – 1.5 × ULN	> 1.5 – 3 × ULN	> 3 – 10 × ULN	> 10 × ULN
Hemoglobin	< LLN – 100 g/L	< 100 – 80 g/L	< 80 g/L	--
White blood cells	< LLN – 3.0 × 10  /L	< 3.0 – 2.0 × 10  /L	< 2.0 – 1.0 × 10  /L	< 1.0 × 10  /L
Absolute Neutrophil Count	< LLN – 1.5 × 10  /L	< 1.5 – 1.0 × 10  /L	< 1.0 – 0.5 × 10  /L	< 0.5 × 10  /L
Platelet count	< LLN – 75.0 × 10  /L	< 75.0 – 50.0 × 10  /L	< 50.0 – 25.0 × 10  /L	< 25.0 × 10  /L
INR	> 1 – 1.5 × ULN	> 1.5 – 2.5 × ULN	> 2.5 × ULN	--
Glucose (high)	> ULN – 8.9 mmol/L	> 8.9 – 13.9 mmol/L	> 13.9 – 27.8 mmol/L	> 27.8 mmol/L
Glucose (low)	< LLN – 3.0 mmol/L	< 3.0 – 2.2 mmol/L	< 2.2 – 1.7 mmol/L	< 1.7 mmol/L
Creatinine	> ULN – 1.5 × ULN	> 1.5 – 3 × ULN	> 3 – 6 × ULN	> 6 × ULN
Creatinine clearance	< LLN – 60 mL/min	< 60 – 30 mL/min	< 30 – 15 mL/min	< 15 mL/min
eGFR (C-MDRD)	< LLN – 60 mL/min/1.73 m 	< 60 – 30 mL/min/1.73 m 	< 30 – 15 mL/min/1.73 m 	< 15 mL/min/1.73 m 
Cholesterol	> ULN – 7.75 mmol/L	> 7.75 – 10.34 mmol/L	> 10.34 – 12.92 mmol/L	> 12.92 mmol/L
Albumin	< LLN – 30 g/L	< 30 – 20 g/L	< 20 g/L	--
Lymphocyte	< LLN – 0.8 × 10  /L	< 0.8 – 0.5 × 10  /L	< 0.5 – 0.2 × 10  /L	< 0.2 × 10  /L
aPTT	> ULN – 1.5 × ULN	> 1.5 – 2.5 × ULN	> 2.5 × ULN	--
Sodium (low)	< LLN – 130 mmol/L	--	< 130 – 120 mmol/L	< 120 mmol/L
Sodium (high)	> ULN – 150 mmol/L	> 150 – 155 mmol/L	> 155 – 160 mmol/L	> 160 mmol/L
Potassium (low)	< LLN – 3.0 mmol/L	--	< 3.0 – 2.5 mmol/L	< 2.5 mmol/L
Potassium (high)	> ULN – 5.5 mmol/L	> 5.5 – 6.0 mmol/L	> 6.0 – 7.0 mmol/L	> 7.0 mmol/L

**Table 11. Definitions of Toxicity Grades 1, 2, 3, and 4 for Laboratory Values (Continued)**

Test	Grade 1	Grade 2	Grade 3	Grade 4
Triglycerides	> 1.71 – 3.42 mmol/L	> 3.42 – 5.7 mmol/L	> 5.7 – 11.4 mmol/L	> 11.4 mmol/L
Magnesium (low)	< LLN – 0.5 mmol/L	< 0.5 – 0.4 mmol/L	< 0.4 – 0.3 mmol/L	< 0.3 mmol/L
Magnesium (high)	> ULN – 1.23 mmol/L	--	> 1.23 – 3.30 mmol/L	> 3.30 mmol/L
CPK	> ULN – 2.5 × ULN	> 2.5 – 5 × ULN	> 5 – 10 × ULN	> 10 × ULN

Assessments of hepatotoxicity will be made based on a single laboratory parameter collected at any post-baseline visit through the Final Treatment visit using the following criteria:

- ALT > 5 × ULN and  $\geq 2 \times$  baseline;
- Total bilirubin  $\geq 2 \times$  ULN and > baseline;
- Total bilirubin  $\geq 2 \times$  ULN and > baseline and direct/total bilirubin ratio > 0.4;
- Increase from nadir by grade in ALT:
  - ALT > 3 – 5 × ULN (Grade 2);
  - > 5 – 20 × ULN (Grade 3);
  - > 20 × ULN (Grade 4).

The direct/ total bilirubin ratio will be calculated using the same date/time sample corresponding to the total bilirubin elevation. For the summary of increase from nadir by grade in ALT, the post-baseline value must represent an increase from the first nadir (including baseline) to be counted, where the grade of the post-baseline value must be more extreme than the grade of the nadir value. First nadir is defined as the last value prior to the first increase. The maximum ratio relative to the ULN will be used to determine if subjects meet the criteria listed above.

Assessments of hepatotoxicity will also be made based on multiple laboratory parameters collected at any post-baseline visit through the Final Treatment visit using the following criterion:

- ALT  $> 3 \times$  ULN (Grade 2+ and increase from nadir grade) and total bilirubin  $\geq 2 \times$  ULN.

For the criterion based on multiple laboratory parameters, the analysis will check to see if the subject meets the ALT and total bilirubin portions of the criterion at any time within the Treatment Period (i.e., draw dates do not need to be concurrent). The maximum ratio relative to the ULN for each parameter will be used to determine if the subject meets the criterion listed above. For ALT, the post-baseline value must represent an increase from the first nadir (including baseline) to be counted. First nadir is defined as the last value prior to the first increase. The grade of the post-baseline ALT value must be at least Grade 2 and more extreme than the grade of the nadir value. For total bilirubin, a subject or event will be counted if the post-baseline laboratory values meet the above criteria regardless of the baseline laboratory value (i.e., the post-baseline laboratory value does not need to be worse than the baseline laboratory value).

